One limitation of current AID systems is that they have no knowledge about the context or environment that a person is currently experiencing. Contextual patterns can potentially improve the performance of an AID by recognizing environments or patterns of living that are related to changes in glucose. The team at OHSU is developing a context-aware glucose prediction algorithm that will capture context data from the patient both indoors and outdoors. This context data will be provided to the algorithm to allow for detecting contextual patterns that might relate to hypo- or hyperglycemia. The goal of this study will be the creation of a data set that will include contextual patterns along with glucose, insulin and physiological data. Participants will complete meals and exercise at specific times. The purpose of the prescribed meals and exercise sessions is to generate ground truth patterns that will be used in the design of the context-aware glucose prediction algorithm.

Primary Objective

- To assess the accuracy of the context-aware glucose prediction by comparing glucose prediction values against the Dexcom G6 CGM values using mean absolute relative error (MARE)
- To assess the accuracy of the context-aware glucose prediction by comparing glucose prediction values against the Dexcom G6 CGM values using mean relative error (MRE).

Study Hypothesis:

- The study hypothesis is that context pattern data will improve the accuracy of the prediction of hypoglycemia and hyperglycemia in the context-aware glucose prediction algorithm.

Primary Endpoints:

- Comparison of the accuracy of hypoglycemia prediction comparing glucose prediction values against the Dexcom G6 CGM values using mean absolute relative error (MARE).
- Comparison of the accuracy of hypoglycemia prediction comparing glucose prediction values against the Dexcom G6 CGM values using mean relative error (MRE).

Study Type

This is a single center randomized prospective study measuring the accuracy of the context-aware glucose prediction against the Dexcom G6 CGM values.

Study Population

[figure not shown]
Study population will be adults with type 1 diabetes, ages 18 – 65 years of age. Older subjects are excluded due to higher risk of unrecognized coronary artery disease. Younger subjects are excluded as it is appropriate to assess safety and efficacy first in the adult population. Thirty subjects will be recruited to participate in studies.

Protocol Summary:

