Statistical methods

The hypothesis of this study is that we will be able to identify contextual patterns in the movement data that will relate to glycemic outcomes. We will use machine learning techniques

including k-means clustering and Gaussian mixture models to group contextual patterns and then relate these groups of patterns with glycemic outcomes including the following:

- Time in hypoglycemia (<70 mg/dL)
- Time in hyperglycemia (>180 mg/dL)
- Time in a target range (70-180 mg/dL)
- Mean glucose
- Glucose variability (standard deviation and coefficient of variance).

We will evaluate if the clusters of contextual patterns are related to differences in glycemic outcome measures using generalized estimating equations, which takes into account correlated data and repeated measures. Data will be analyzed using an intention-to-treat analysis and missing sensed glucose values will be interpolated for up to 20 min segments.

Confidentiality and Protection of Human Subjects

RISKS and BENEFITS

Risks: The risks of the protocol procedures are considered minor. Subjects will be managing their own blood glucose as they normally would.

Risks from exercise include falls, sprains, bruises, very low risk of bone fractures and head trauma. The likelihood of significant harm is quite low.

There is a small risk of sensor fracture, and in such a case, a piece of the sensor could be left in the tissue after sensor removal. For this reason, the study investigator will inspect each removed sensor for the possibility of breakage or fracture. Any evidence of sensor breakage will be recorded and reported to the sensor company.

Benefits: The subject may not directly benefit from being in this study; however, their participation may help to advance automated insulin decision support software.

COSTS:

Subjects will receive \$500 for completion of all study visits. If subjects withdraw early from the study, compensation will be given as follows: \$125 per 7 study days in the study. If the subject completes a partial week, the subject will also receive \$125 for the partial week. There is no compensation for the screening visit. Additional reimbursement will be available for participants who complete protocol requirements to help compensate for their time. The payment amount will be specified in the informed consent form.

Monitoring Entity:

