The de-identified data collected during this study will be used for analysis of the primary and secondary endpoints listed in this protocol. This data will also be stored in the OregonAPC repository according to IRB protocol 19858. During screening, participants may sign the consent form to store their study data in the data repository. The data to be collected includes: 1) glucose sensor data, 2) blood glucose data, 3) insulin data, 4) physical activity data, and 5) food and exercise data. All data, except for blood glucose and insulin, is aggregated by the DEXI app. The blood glucose data is collected through downloading the Contour Next BG meters and exporting data as an excel file. The insulin data is collected by downloading the subject's insulin pump. There are no biological specimens collected during this study.

Monitoring Procedures:

This protocol is written in accordance with the principles established by the 18th World Medical Assembly General Assembly (Helsinki, 1964) and amendments and clarifications adopted by the 29th (Tokyo, 1975), 35th (Venice, 1983), 41st (Hong Kong, 1989), 48th (Somerset West, South Africa, 1996), 52nd (Edinburgh, 2000), 53rd (Washington, 2002), 55th (Tokyo, 2004), 59th (Seoul, 2008), and 64th (Brazil, 2013) General Assemblies. The investigator will ensure that the study described in this protocol is conducted in full conformance with those principles, the protocol, current FDA regulations, ICH Good Clinical Practices (GCP) guidelines, Good Laboratory Practices (GLP) guidelines, local ethical and regulatory requirements, including the Federal Food, Drug and Cosmetic Act, U.S. applicable Code of Federal Regulations (title 21), any IEC requirements relative to clinical studies.

Should a conflict arise, the investigator will follow whichever law or guideline affords the greater protection to the individual subject. The investigator will also ensure thorough familiarity with the appropriate use and potential risks of use of the study device, as described in this protocol, prior to the initiation of the study.

Unanticipated problems will be detected by reviewing descriptions of known or foreseeable adverse events and risks in the IRB-approved research protocol and the current IRB approved consent form, any underlying disease or conditions of the subject experiencing the adverse

event, a careful assessment of whether the adverse event is related or possibly related to the subject's participation in the study.

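### The hypothesis, objectives and primary endpoints give three different scopes for the same two accuracy metrics, and no section says which glucose readings enter MARE or MRE

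*Combined protocol and SAP*

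**What the plan says.** The opening part of the protocol describes the accuracy comparison in four places, with three scopes.

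- **Study Hypothesis:** "context pattern data will improve the accuracy of the prediction of hypoglycemia and hyperglycemia". Lows and highs are both covered.
- **Primary Objective:** "To assess the accuracy of the context-aware glucose prediction by comparing glucose prediction values against the Dexcom G6 CGM values", once by MARE and once by MRE. No range is given.
- **Study Type:** "measuring the accuracy of the context-aware glucose prediction against the Dexcom G6 CGM values". Again no range.
- **Primary Endpoints:** "Comparison of the accuracy of hypoglycemia prediction comparing glucose prediction values against the Dexcom G6 CGM values using mean absolute relative error (MARE"), and "Comparison of the accuracy of hypoglycemia prediction comparing glucose prediction values against the Dexcom G6 CGM values using mean relative error (MRE"). Both name hypoglycemia only.

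Statistical methods gives cut-offs of <70 and >180 mg/dL, but for another purpose. They define time-in-range outcomes in an analysis that will cluster movement patterns and "relate these groups of patterns with glycemic outcomes including the following". MARE, MRE and prediction error are not mentioned there. The sensor levels of <70 and >250 mg/dL in the Protocol Summary and the start-up visit are alarm levels that prompt a fingerstick, not scoring ranges.

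Recording of Data says the data will be "used for analysis of the primary and secondary endpoints listed in this protocol", but no secondary endpoint appears in the text available for review.

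**The concern.** A primary endpoint should tell the analyst which observations are scored. Here the term hypoglycemia prediction could mean readings where the CGM value is low, readings where the predicted value is low, or loosely all readings. The protocol does not choose between them.

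Two things are at stake. First, if the endpoints are followed as worded, the hyperglycemia half of the hypothesis has no primary result, although the study prescribes a weekly high-carbohydrate dinner and the introduction treats highs and lows alike. Second, an unfixed range can be settled after results are seen, and the possible ranges answer different questions.

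**Working it through.** **No plan figure to reproduce.** The documents give no glucose distribution, expected MARE, error SD or power calculation. The text comparison above carries the inconsistency; the numbers below only show whether the choice of range matters.

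**Definitions.** For CGM value G and prediction P, the relative error is r = (P − G)/G. MARE is the mean of |r|. MRE is taken as the mean of signed r, which its name suggests; no formula is given.

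**By construction, with no assumptions.** If only pairs with G < 70 are scored, changing predictions where G > 180 changes no term in the average. MARE and MRE cannot move, whether highs are predicted better or worse.

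**Illustration (all inputs assumed).** G is lognormal with mean 150 and SD 55 mg/dL, clipped to 40–400. P is the conditional mean given a signal with R2 0.9 on the log scale. Four million readings were simulated.

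- σ² = ln(1 + (55/150)²) = 0.126, so σ = 0.355; μ = ln 150 − 0.063 = 4.948.
- Share below 70: Φ((ln 70 − 4.948)/0.355) = Φ(−1.97), about 2.5%. Share above 180: about 24.5%.

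| Predictor | MARE, all | MARE, CGM <70 | MARE, CGM >180 |
|---|---|---|---|
| Base | 9.1% | 12.3% | 8.9% |
| Errors halved where CGM >180 | 8.0% | 12.3% | 4.4% |
| Capped at 180 (no high ever predicted) | 11.3% | 12.3% | 19.0% |
| Floored at 70 (no low ever predicted) | 9.2% | 19.5% | unchanged |

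The reason is the weight of each range. Lows contribute about 0.0245 × 12.3 = 0.30 of the 9.07 percentage points of all-range MARE (about 3%). Highs contribute about 0.245 × 8.86 = 2.17 (about 24%). Halving every error on lows therefore takes all-range MARE only from 9.07% to 8.92%.

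**Sensitivity to the assumptions.** Flooring at 70 moves all-range MARE from 12.96% to 13.05% at R2 0.8 and from 4.02% to 4.30% at R2 0.98. At R2 0.9 it moves from 9.3% to 9.4% with mean 160/SD 60, and from 8.0% to 8.1% with mean 140/SD 45. With 10% error that is unbiased given the reference, it moves from 8.0% to 8.1%. The insensitivity to lows holds throughout.

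**Can the ranges disagree in direction?** They can under a deliberate bias. Multiplying every base prediction by 0.9 improves MARE at CGM <70 (12.3% to 8.6%) but worsens it where the prediction is <70 (9.0% to 11.3%) and over all readings (9.1% to 11.3%). Sensitivity for <70 rises from 59% to 85% while PPV falls from 80% to 56%, so lows really are caught, at the price of false alarms. The effect depends on the assumed predictor: at R2 0.95 MARE at CGM <70 goes from 7.5% to 7.7%, and with 10% error unbiased given the reference it worsens from 8.0% to 11.2%. A genuine gain in R2 from 0.90 to 0.95 improves every measure examined.

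**The case against.** A protocol may hypothesise about lows and highs and make only lows primary, and a narrower primary endpoint is not in itself an error. Hypoglycemia prediction may also be loose wording for all-range accuracy, since the objectives and Study Type describe the same comparison without a range. On that reading highs are scored, and all-range MARE does register the capped predictor (9.1% to 11.3%). The stated goal is to build a data set for an algorithm still in development. The simulation inputs are not the sponsor's, and the cap and floor are contrived.

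Much of this stands. It rules out inferring that the plan never scores high readings: the unrestricted objectives would include them. It also does not rescue the text. If lows were deliberately chosen, the objectives should say so and the range should be defined. If all readings were meant, the endpoints are miswritten and the result would say little about the lows they name.

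A reader might also infer that the plan is wrong to omit detection or false-alert endpoints. The documents do not support that. The objectives choose continuous error, and nothing promises an alert or classifier. Such measures would be useful, but their absence is not an error. Nor is MRE out of place: as a signed measure it shows bias beside MARE, and only reading it alone as accuracy would mislead.

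**Conclusion.** The inconsistency is real and is established by the text alone: three scopes for one pair of metrics, no stated scoring range, and no analysis of either metric in Statistical methods. That scoring only lows hides any change on highs is true by construction. That scoring all readings nearly hides lows (9.1% to 9.2% when no low is ever predicted) rests on assumed inputs, but held across the distributions and error models tried.

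A reader might go further and expect the conclusion about context to reverse with the range chosen. That is possible but not shown to be likely: the only reversal found came from a deliberate bias and was gone by R2 0.95. The absence of secondary endpoints is judged on the supplied text only. This should be corrected before prediction results are examined.

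**What to change.** 1. Reconcile Primary Endpoints with Primary Objective, Study Type and Study Hypothesis.
2. Name one primary scored range in advance, defined by the CGM reference value rather than the prediction. All paired readings would match the objectives.
3. Report MARE, with MRE beside it as the bias measure, separately for CGM <70 and CGM >180 mg/dL as prespecified key results. These are the protocol's own cut-offs. Give the formula for each metric.
4. Give every result with and without context data, since the hypothesis is one of improvement.
5. Add this analysis to Statistical methods, which at present covers only the cluster analysis. Changing the endpoint wording alone would leave the primary endpoints without an analysis.
6. Optionally, add sensitivity with PPV or false alerts for <70 and >180 mg/dL as secondary summaries.

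The cost is revised wording and a few more summaries from the same predictions, with no new data. The downside is a longer endpoint list, and the <70 results will be imprecise because few readings are likely to be that low.

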Subject Criteria

Inclusion Criteria:

1. Diagnosis of type 1 diabetes mellitus for at least 1 year.
2. Male or female subjects 18 to 65 years of age.
3. Physically willing and able to perform 30 min of exercise (as determined by the investigator after reviewing the subject's activity level).
4. Current use of an insulin pump for at least 3 months.
5. Able and willing to count

[figure not shown]

Figure 2: (a) MotioWear tag based indoor/outdoor tracking and context awareness system. (b) MotioLab software that can be used to do real-time tracking indoors and outdoors. (c) Beacons are placed around the home, creating a wireless mesh that the wearable communicates with. A smart-phone app identifies key regions of interest.

carbohydrates during study period as determined by the investigator after reviewing participant's insulin pump download.

6. A1C <10.5% at the time of screening.
7. Has a smart phone.
8. Willingness to follow all study procedures, including attending all clinic visits.
9. Willingness to sign informed consent and HIPAA documents.

Exclusion Criteria:

1. Female of childbearing potential who is pregnant or intending to become pregnant or breast-feeding, or is not using adequate contraceptive methods. Acceptable contraception includes birth control pill / patch / vaginal ring, Depo-Provera, Norplant, an IUD, the double barrier method (the woman uses a diaphragm and spermicide and the man uses a condom), or abstinence.
2. Any cardiovascular disease, defined as a clinically significant EKG abnormality at the time of screening or any history of: stroke, heart failure, myocardial infarction, angina pectoris, or coronary arterial bypass graft or angioplasty. Diagnosis of 2nd or 3rd degree heart block or any non-physiological arrhythmia judged by the investigator to be exclusionary.
3. Renal insufficiency (GFR < 60 ml/min, using the MDRD equation as reported by the OHSU laboratory).
4. Liver failure, cirrhosis, or any other liver disease that compromises liver function as determined by the investigator.
5. Hematocrit of less than 36% for men, less than 32% for women.
6. History of severe hypoglycemia during the past 12 months prior to screening visit or hypoglycemia unawareness as judged by the investigator. Subjects will complete a hypoglycemia awareness questionnaire. Subjects will be excluded for four or more R responses.
7. Adrenal insufficiency.
8. Any active infection.
9. Known or suspected abuse of alcohol, narcotics, or illicit drugs.

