10. Seizure disorder.
11. Active foot ulceration.
12. Peripheral arterial disease.
13. Major surgical operation within 30 days prior to screening.
14. Use of an investigational drug within 30 days prior to screening.
15. Chronic usage of any immunosuppressive medication (such as cyclosporine, azathioprine, sirolimus, or tacrolimus).
16. Bleeding disorder or platelet count below 50,000.
17. Current administration of oral or parenteral corticosteroids.
18. Any life threatening disease, including malignant neoplasms and medical history of malignant neoplasms within the past 5 years prior to screening (except basal and squamous cell skin cancer).
19. Beta blockers or non-dihydropyridine calcium channel blockers.

20. Current use of any medication intended to lower glucose other than insulin (ex. use of liraglutide).
21. A positive response to any of the questions from the Physical Activity Readiness Questionnaire with one exception: subject will not be excluded if he/she takes a single blood pressure medication that doesn't impact heart rate and blood pressure is controlled on the medication (blood pressure is less than 140/90 mmHg).
22. Any chest discomfort with physical activity, including pain or pressure, or other types of discomfort.
23. Any clinically significant disease or disorder which in the opinion of the Investigator may jeopardize the subject's safety or compliance with the protocol.

Subject Recruiting:

Subjects will be recruited from OHSU clinics, from flyers to be posted in approved places at OHSU or posted on the web to the clinical trials page for the OHSU Schnitzer Diabetes Clinic, to the Clinic's facebook group, ads on facebook, electronic newsletter or from the OHSU Subject Recruitment website. Handouts may also be made available to faculty at Providence, Tuality, Kaiser and Legacy to pass along to patients/participants who show interest in the study. Records from OHSU Schnitzer Diabetes Clinic patients may be screened to find potential subjects. Subjects will also be recruited from a list of subjects who participated in past OHSU studies who have agreed to be contacted regarding future studies involving Drs. [name] or [name], from the OHSU diabetes research registry and/or www.clinicaltrials.gov. Non-English speaking subjects will not be recruited since this protocol would require the use of medical devices and mobile software that do not have non-english versions available.

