Up to 75 subjects may be screened in this study. Goal enrollment is 30 subjects.

Withdrawal Criteria

The subject may withdraw at will at any time or at the discretion of the Investigator.

A subject must be withdrawn if the following applies:

1. Hypoglycemia during the treatment period posing a safety problem as judged by the investigator.
2. Hyperglycemia during the treatment period posing a safety problem as judged by the investigator.
3. Protocol deviation having influence on efficacy or safety data as judged by the Investigator.
4. Substantial and repeated non-compliance with trial procedures.
5. Pregnancy.
6. Intention of becoming pregnant.

Visit Procedures

Staff will confirm participant and household do not have COVID-19 or symptoms of COVID-19 prior to conducting any face-to-face visits. In order to minimize face to face contact with participants per OHSU Covid-19 policy, there is the option to complete some visits virtually.

Screening (Visit 1)

Screening will take place within 12 weeks prior to Visit 2. All screening visits will take place at OHSU's Oregon Clinical Translational Research Institute (OCTRI) outpatient clinic, the

Biomedical Engineering Point of Care (BME POC) Laboratory or at the Harold Schnitzer Diabetes Health Center. The subject will be sent the consent form prior to the screening by email so that they can have time to read it fully at their leisure and prepare any questions they might have. Upon arrival at the clinic and prior to any procedures, study staff will explain the study, give the subject ample time to ask questions and consider participation, and ensure that subject voices understanding of the informed consent and study requirements. To minimize the possibility of coercion and to ensure that subject is signing the appropriate version of consent, an informed consent checklist will be used by study staff. After the subject has signed the consent, a copy of the consent/authorization form will be given to the subject. The original will be kept for the source document.

A capillary blood glucose (CBG) will be obtained and measured by a Contour Next glucose meter and recorded after consenting. Prior to measurement of any blood samples, the meter will undergo quality control testing with two different glucose levels, one high and one low, and both values must fall within the accepted range for a meter to be used.

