Study personnel will review medical history, and medications. Height, weight, pulse, and blood pressure will be obtained. A study investigator will perform a physical examination, excluding breast and pelvic exams. Females of child-bearing potential will take a urine pregnancy test, which must be negative to participate. A venous blood sample will be taken for the following tests: hemoglobin A1C, complete blood count, complete metabolic set (including creatinine, liver set, and electrolytes). If subjects have had any of the aforementioned labs performed within the 3 months prior to the screening visit and we can access the results, a venous blood sample will not be taken for that test. An EKG will be completed. A study investigator will assess inclusion/exclusion criteria and review the subject's medical record for clarification as needed. The participant's insulin pump will be downloaded to determine if they are counting carbohydrates for meals. A three-digit subject ID number will be assigned to the subject. One research staff member and a study investigator will on site for this visit. When the risk of Covid-19 is considered to be significant and OHSU is on modified operations, only one staff member will be in the room with the participant at a time and the only time staff will have to be within 6 feet of the participant is when the study investigator is completing the physical exam and when research staff is completing the EKG and drawing blood for screening labs.

This visit will take approximately 1.5 hours.

Study Start-up Visit (Visit 2):

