At this visit, the devices will be turned in and the subject's insulin pump will be downloaded. A study investigator will be available for consult if needed regarding insulin management. The Dexcom sensor will be removed from the subject. The sensor site will be inspected for signs of irritation or infection. In addition, the sensor will be inspected for the possibility of breakage or fracture. If there is any evidence of sensor breakage, it will be recorded. If an area of inflammation of 1 cm or greater exists around the point of insertion, a de-identified photograph will be taken of the area and the subject will return 1-3 days later for a follow-up visit. If the study coordinator notes any significant redness or swelling, the study investigator will be contacted. A capillary blood glucose value will be taken immediately prior to discharging the subject. Subjects will be given oral carbohydrate for values below 85 mg/dl, and will be instructed to give an injection of aspart insulin if deemed appropriate by the study investigator for values above 150 mg/dl. This visit will take approximately 1 hour.

There is the option to complete this visit by Webex. Participants will be given shipping boxes for sending all devices back. Participants will be given a checklist of equipment to return with instructions on how to uninstall the tracking devices. Participants will connect with a study coordinator virtually to complete the visit.

If a study visit is stopped prematurely the subject will be asked if they can repeat the study visit that was terminated early with additional compensation provided. Repeating the study visit will be optional. If the study period is paused for a period of time, such as if the patient begins taking a medication that impacts glucose like steroids, the participant may be asked if they can repeat that part of the study period with additional compensation provided.

Cleaning and Disinfecting

All devices will be cleaned and disinfected between subjects. The Dexcom G6 transmitters, MotioWear devices and physical activity monitor will be cleaned by study staff. Technicians who are disinfecting units will wash hands thoroughly and wear gloves. All items will undergo intermediate-level disinfection using SANI-CLOTH AF3 Germicidal disposable wipes. The disinfectant will be applied and allowed to air dry. After disinfection, when the units are completely dry, they will be placed in a sealed bag labeled with subject information.

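### The look-backs in exclusions 6, 13 and 14 end at screening, up to 84 days before Visit 2, and no eligibility re-check is listed at Visit 2

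*Combined protocol and SAP*

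**What the plan says.** Three exclusion criteria have a look-back that stops at screening:

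- Exclusion 6: "History of severe hypoglycemia during the past 12 months prior to screening visit".
- Exclusion 13: "Major surgical operation within 30 days prior to screening".
- Exclusion 14: "Use of an investigational drug within 30 days prior to screening".

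The interval to the start is set under Visit Procedures, Screening (Visit 1): "Screening will take place within 12 weeks prior to Visit 2".

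The same section lists the history and medication review, the physical examination, EKG, laboratory tests, urine pregnancy test and the investigator's assessment of the criteria. None of these is listed again.

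The Study Start-up Visit (Visit 2) section covers device set-up and training, a lifestyle questionnaire on exercise habits and glucose management, exercise and meal instructions, and a COVID-19 symptom screen. It mentions no update of medications or history, no pregnancy check and no confirmation of eligibility, either in person or by Webex.

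Exclusions 1 (pregnancy), 17 (corticosteroids), 19 (beta blockers and certain calcium channel blockers) and 20 (non-insulin glucose-lowering drugs) carry no screening date.

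**The concern.** Exercise and data collection begin at Visit 2, not at screening. A washout or look-back is meant to describe the subject's condition at the start. When it stops at screening and the start may be 12 weeks later, it says nothing about the interval closest to the start.

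Two separate weaknesses follow. For exclusions 6, 13 and 14, an operation, an investigational drug or a severe hypoglycemic episode after screening is outside the dated wording itself. For pregnancy and the excluded drugs, the wording still bars the subject, but no listed step would bring the change to light.

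What is at stake is mainly safety and clean eligibility: a subject with a recent event of the kind the protocol meant to screen out could start the home exercise sessions. Interval exposure to an investigational drug is plausible, because Subject Recruiting draws on past study participants and a diabetes research registry, but the documents give no rate. The protocol itself treats a change of medication as relevant once the study is running: the study period may be paused "if the patient begins taking a medication that impacts glucose like steroids". That provision concerns a drug begun during the study period. It is not a check for one begun in the weeks before.

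**Working it through.** The plan gives no figure of its own here, so there is none to reproduce. The check is date arithmetic.

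**Inputs**
- Maximum interval from screening to Visit 2: 12 weeks (Screening, Visit 1).
- Look-backs: 30 days (exclusions 13 and 14) and 12 months, taken as 365 days (exclusion 6).
- One pregnancy test, at screening. Time on study: 28 days.

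**1. Maximum gap.** g = 12 × 7 = 84 days.

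**2. The 30-day look-backs.** They cover days g to g + 30 before Visit 2. The part of the last 30 days before Visit 2 that they cover is max(0, 30 − g).

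| Gap g (days) | Window covered (days before Visit 2) | Days covered of the last 30 |
|---|---|---|
| 0 | 0 to 30 | 30 |
| 14 | 14 to 44 | 16 |
| 30 | 30 to 60 | 0 |
| 84 | 84 to 114 | 0 |

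The maximum gap is not needed for the look-backs to lose all cover of the final 30 days. Any gap of 30 days or more is enough.

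**3. The 12-month look-back.** Uncovered share of the year before Visit 2 at the maximum gap: 84 / 365 = 0.230, or 23%. These are the most recent 84 days of that year.

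**4. Age of the pregnancy test.** At Visit 2: up to 84 days. At Day 28: 84 + 28 = 112 days.

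**5. Dated and undated criteria side by side**

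| Criterion | Dated to screening? | Event after screening |
|---|---|---|
| 6, severe hypoglycemia | Yes | Outside the look-back |
| 13, major surgery | Yes | Outside the look-back |
| 14, investigational drug | Yes | Outside the look-back |
| 1, 17, 19, 20 (pregnancy, excluded drugs) | No | Still excluded, but no listed step to detect it |

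With the look-backs ending at Visit 2, the uncovered interval falls from up to 84 days to 0. The enrolment goal and the analysis are unaffected.

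**The case against.** The strongest reply is that the protocol is not limited to its dated clauses. Exclusion 23 lets the investigator exclude for any clinically significant condition that may jeopardise safety or compliance. Exclusion 8 (active infection), the unawareness part of exclusion 6 and inclusion 3 (fitness for 30 minutes of exercise) carry no date either. Subjects may be withdrawn at the investigator's discretion, pregnancy requires withdrawal, staff make contact every 7 days, and glucose is checked before each exercise session. Start-up visit and Concomitant Medications case report forms exist, and their content is not in the documents, so a check may take place in practice. No investigational treatment is given, and the protocol rates procedure risks as minor.

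Most of this stands, and it keeps the point modest. It does not remove it. The general clauses depend on judgement, and the only listed assessment of the criteria is at Visit 1. The contacts and glucose checks come after the start. Withdrawal for pregnancy has no later test behind it.

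A further objection is that a re-check at Visit 2 would suffice without re-anchoring. For exclusions 6, 13 and 14 it would not settle the matter: checked against the present wording, an event after screening still falls outside the look-back.

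A reader might also infer that a subject newly pregnant or newly on an excluded drug would meet every criterion. That is not so: exclusions 1, 17, 19 and 20 are undated, and such a subject remains ineligible.

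**Conclusion.** The point holds for exclusions 6, 13 and 14, and as a missing detection step for exclusions 1, 17, 19 and 20. Up to 84 days before the start lie outside the three dated look-backs. The two 30-day look-backs cover none of the final 30 days once the gap reaches 30 days, and 23% of the year before Visit 2 escapes the severe-hypoglycemia look-back at the maximum gap. It is worth correcting, but it does not undermine the study.

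The 84-day, 23% and 112-day figures are worst cases, since the documents give no distribution of actual gaps. The conclusion also assumes that the listed Visit 2 procedures are complete.

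Three wider readings are tempting but not supported:

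- **Laboratory results.** Inclusion 6 asks for "A1C <10.5% at the time of screening", while the screening section waives a new sample "If subjects have had any of the aforementioned labs performed within the 3 months prior to the screening visit" and the results are accessible. A reader might see a contradiction. The waiver reads as the stated rule for obtaining the screening value, so the two are compatible.
- **Malignancy.** Exclusion 18 also has a look-back ending at screening ("medical history of malignant neoplasms within the past 5 years prior to screening"), but its limb on life-threatening disease, which includes malignancy, is undated. A new malignancy is therefore still excluded.
- **Bias in the results.** A reader might infer that undetected drugs or events would distort MARE, MRE or the context clusters. Nothing in the documents shows the direction or size of such an effect, and none is claimed here.

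**What to change.** 1. In exclusions 6, 13 and 14, end the look-back at Visit 2, or at both screening and Visit 2. Anchoring to both keeps the present restriction at screening as well. Anchoring to Visit 2 alone would admit some subjects whose event was shortly before screening but long before the start.
2. Add to the Visit 2 procedures, including the Webex version, a brief documented re-confirmation of eligibility before randomisation. Questions suffice: current medications, surgery since screening, infection, severe hypoglycemia, use of an investigational product, and pregnancy status or intent.

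The cost is a wording change and a few minutes at an existing visit, with an occasional late screen failure. Up to 75 subjects may be screened for a goal of 30, which leaves room for some of these.
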